Appendix 17.4. Electrocardiograms (If applicable)

• If the participant is unable to visit the study site for ECGs, the participant may visit an alternative facility to have the ECGs performed. Qualified study site personnel must order, receive, and review results.

Appendix 17.5. Adverse Events and Serious Adverse Events

- If a participant has COVID-19 during the study, this should be reported as an adverse event (AE) or serious adverse events (SAE) and appropriate medical intervention provided. There is a potential risk of increased susceptibility to viral infections with IFNβ blockade as with any antagonist of Type 1 interferon signaling (eg, anti-IFNAR1, anti-IFNα, JAK inhibitors). Viral monitoring will be conducted as a precautionary measure to ensure participant safety. Details can be found in the trial protocol as well as the investigators brochure. Temporary discontinuation of the study intervention may be medically appropriate until the participant has recovered from COVID-19.
- It is recommended that the investigator discuss temporary or permanent discontinuation of study intervention with the study medical monitor.

CCI		
	CCI	
	CCI	
CCI		
CCI		, Cana

Appendix 19. Muscle Enzymes

IMACS FORM 06: SERUM LEVELS OF MUSCLE ENZYMES

Subject's IMACS number Date of assessment (mm/dd/yy) Assessment number			
Blood laboratories:	Result	Normal Range	
Creatine kinase (IU/L)			
Aldolase (IU/L)			
SGOT (IU/L)			_
SGPT (IU/L)			_
LDH (IU/L)			
Creatinine (mg/dl)			

Appendix 20. MDAAT

IMACS FORM 07a: MYOSITIS DISEASE ACTIVITY ASSESSMENT TOOL - 2005, Version 2

Subject S IMAGS humber ASSESSOR Date AssessedASSESSINENT humber.	Subject's IMACS number:	ASSESSOR:	Date Assessed:	Assessment number:
--	-------------------------	-----------	----------------	--------------------

Constitutional (Abs Disease Activity	sent)	(Maximum)	Exam Sever	n ples of re fatigu d and a	f maxim ie or ma n inabilit	al score laise res y to perf	e ulting in orm self	being bed care
1. Pyrexia – documented fev	ver > 38° Celsius		0	1	2	3	4	NA
2. Weight loss - unintentiona	al > 5%		0	1	2	3	4	NA
3. Fatigue/malaise/lethargy			0	1	2	3	4	NA
Cutaneous Disease Activity	sent)	(Maximum)	Exam - Ulce - Exte	ples of eration t ensive e	f maxim o muscle rythrode	al score e, tendor rma	e n or bon	e;
4. Cutaneous ulceration			0	1	2	3	4	NA
5. Erythroderma			0	1	2	3	4	NA
6. Panniculitis			0	1	2	3	4	NA
Erythematous rashes:								
a. with secondary chang	ges (e.g. accompanied by erosions, vesiculobullous cl	nange or necrosis)	0	1	2	3	4	NA
b. without secondary characteristics	nanges		0	1	2	3	4	NA
Heliotrope rash			0	1	2	3	4	NA
9. Gottron's papules/sign			0	1	2	3	4	NA
10. Periungual capillary chang	ges		0	1	2	3	4	NA
11. Alopecia:								
a. Diffuse hair loss			0	1	2	3	4	NA
b. Focal, patchy with ery	/thema		0	1	2	3	4	NA
12. Mechanics hands			0	1	2	3	4	NA

IMACS Form 07a: Myositis Disease Activity Assessment Tool – 2005, Version 2, updated 2015

Page 1 of 3

Skeletal Disease Activity	(Absent)	(Maximum)	cm	Exam Sever (bedri	ples o e arthri dden, i	f maxim itis with e nability f	al score extreme or self c	₽ loss of f are)	function
13. Arthritis:									
a. Severe active po	lyarthritis			0	1	2	3	4	NA
b. Moderately activ	e arthritis			0	1	2	3	4	NA
c. Mild arthritis				0	1	2	3	4	NA
14. Arthralgia				0	1	2	3	4	NA
Gastrointestinal Disease Activity	(Absent)	(Maximum)	cm	Exam Major intens	ples o abdom ive car	f maxim ninal cris e	al score is requir	e ing surg	ery or
15. Dysphagia:									
a. Moderate/severe	dysphagia			0	1	2	3	4	NA
b. Mild dysphagia				0	1	2	3	4	NA
16. Abdominal pain rela	ted to the myositis disease process:								
a. Severe				0	1	2	3	4	NA
b. Moderate				0	1	2	3	4	NA
c. Mild				0	1	2	3	4	NA
Pulmonary	(Absent)	(Maximum)		Exam Active	ples o interst	f maxim itial lung	al score disease quiring v	e or resp /entilator	piratory ry support
Disease Activity			cm	musc	e weak	ness ree			
Disease Activity 17. Respiratory muscle	weakness without interstitial lung disease (ILD):		cm	musc	e weak	ness ree			
Disease Activity 17. Respiratory muscle a. Dyspnea at rest	weakness without interstitial lung disease (ILD):		cm	musc 0	e weak	2	3	4	NA
Disease Activity 17. Respiratory muscle a. Dyspnea at rest b. Dyspnea on exer	weakness without interstitial lung disease (ILD): tion		cm	musc 0 0	e weak 1 1	2 2 2	3 3	4 4	NA NA
Disease Activity 17. Respiratory muscle a. Dyspnea at rest b. Dyspnea on exer 18. Active reversible II Read glossary for si	weakness without interstitial lung disease (ILD): tion .D (i.e. not just ventilatory abnormalities due to pulmonary fi roring pulmonary function tests and score each item below	brosis): (a,b and c).	cm	0 0	le weak 1 1	2 2 2	3 3	4 4	NA NA
Disease Activity 17. Respiratory muscle a. Dyspnea at rest b. Dyspnea on exer 18. Active reversible II Read glossary for si a. Dyspnea or coug	weakness without interstitial lung disease (ILD): tion .D (i.e. not just ventilatory abnormalities due to pulmonary fi coring pulmonary function tests and score each item below (h due to ILD	ibrosis): (a,b and c).	cm	0 0 0	le weak 1 1	2 2 2	3 3 3	4 4 4	NA NA NA
Disease Activity 17. Respiratory muscle a. Dyspnea at rest b. Dyspnea on exer 18. Active reversible II Read glossary for s a. Dyspnea or coug b. Parenchymal abb ground glass sha	weakness without interstitial lung disease (ILD): tion D (i.e. not just ventilatory abnormalities due to pulmonary fi coring pulmonary function tests and score each item below (h due to ILD iormalities on chest x-ray or high resolution CT scan (HRC1 dowing on HRCT	ibrosis): (a,b and c). [) and/or	cm	0 0 0 0	1 1 1 1 1	2 2 2 2 2	3 3 3 3	4 4 4 4	NA NA NA
Disease Activity 17. Respiratory muscle a. Dyspnea at rest b. Dyspnea on exer 18. Active reversible II Read glossary for s a. Dyspnea or coug b. Parenchymal abl ground glass sha c. Pulmonary Funct	weakness without interstitial lung disease (ILD): tion D (i.e. not just ventilatory abnormalities due to pulmonary fi coring pulmonary function tests and score each item below (h due to ILD ormalities on chest x-ray or high resolution CT scan (HRCT dowing on HRCT ion Tests: ≥ 10% change in FVC OR ≥ 15% change in DLC	brosis): (a,b and c). () and/or	cm	0 0 0 0 0	1 1 1 1 1	2 2 2 2 2 2 2	3 3 3 3 3	4 4 4 4	NA NA NA NA
Disease Activity 17. Respiratory muscle a. Dyspnea at rest b. Dyspnea on exer 18. Active reversible II Read glossary for s a. Dyspnea or coug b. Parenchymal abo ground glass sha c. Pulmonary Funct 19. Dysphonia: a. Moderate to sev b. Mild	weakness without interstitial lung disease (ILD): tion D (i.e. not just ventilatory abnormalities due to pulmonary fi coring pulmonary function tests and score each item below (h due to ILD iormalities on chest x-ray or high resolution CT scan (HRC1 dowing on HRCT ion Tests: ≥ 10% change in FVC OR ≥ 15% change in DLC ere	brosis): (a,b and c). () and/or ()	cm	0 0 0 0 0 0	le weak 1 1 1 1 1 1 1	2 2 2 2 2 2 2 2 2 2 2 2 2	3 3 3 3 3 3 3 3	4 4 4 4 4 4 4	NA NA NA NA NA NA

IMACS Form 07a: Myositis Disease Activity Assessment Tool – 2005, Version 2, updated 2015

Page 2 of 3

Disease Activity Myocardits, percardits or serving intensive care unit 20. Pericarditis 0 1 2 3 21. Myocarditis 0 1 2 3 22. Arrhythmia: 0 1 2 3 23. Sinus tachycardia 0 1 2 3 23. Sinus tachycardia 0 1 2 3 Other Disease (Absent) (Maximum) Examples of maximal score Extreme disease activity with 1 2 3	4 4 4 4 4 4 2 major ir	nythmia NA NA NA NA NA mpact on			
20. Pericarditis 0 1 2 3 21. Myocarditis 0 1 2 3 22. Arrhythmia: 0 1 2 3 23. Sinus tachycardia 0 1 2 3 23. Sinus tachycardia 0 1 2 3 Other Disease (Absent) (Maximum) Examples of maximal score Activity (Absent) (Maximum) Examples of maximal score	4 4 4 4 2 . major in	NA NA NA NA MA mpact on			
21. Myocarditis 0 1 2 3 22. Arrhythmia: 0 1 2 3 a. Severe arrhythmia, except sinus tachycardia 0 1 2 3 b. Other arrhythmia, except sinus tachycardia 0 1 2 3 23. Sinus tachycardia 0 1 2 3 Other Disease Activity (Maximum) Examples of maximal score Extreme disease activity with Extreme disease activity with	4 4 4 i major in	NA NA NA NA			
22. Arrhythmia: 0 1 2 3 a. Severe arrhythmia 0 1 2 3 b. Other arrhythmia, except sinus tachycardia 0 1 2 3 23. Sinus tachycardia 0 1 2 3 Other Disease Activity	4 4 4 i major ir	NA NA NA			
a. Severe arrhythmia 0 1 2 3 b. Other arrhythmia, except sinus tachycardia 0 1 2 3 23. Sinus tachycardia 0 1 2 3 Other Disease Activity (Absent) (Maximum) Examples of maximal score Extreme disease activity with	4 4 4 1 major in	NA NA NA mpact on			
b. Other arrhythmia, except sinus tachycardia 23. Sinus tachycardia 0 1 2 3 0 1 2 3 Other Disease Activity Activity Activity	4 4 e 1 major ir	NA NA mpact on			
23. Sinus tachycardia 0 1 2 3 Other Disease Activity (Maximum) Examples of maximal score Extreme disease activity with	4 e 1 major ii	NA mpact on			
Other Disease (Absent) (Maximum) Examples of maximal score Extreme disease activity with	e 1 major i	mpact on			
Activity Extreme disease activity with	n major i	mpact on			
i i i i i i i i i i i i i i i i i i i					
24. Specify: 0 1 2 3	4	NA			
Extramuscular (Absent) (Maximum)		U			
Global Overan evaluation for diseases	e activity	y in all			
Assessment (EXCLUDING MUSCLE DIS	EASE A	ACTIVITY)			
(Absent) (Maximum) Examples of maximal score	e				
Muscle Disease Severe muscle weakness res	Severe muscle weakness resulting in being bed bound and an inability to perform self care				
bound and an inability to perform					
25. Myositis:					
a. Severe muscle inflammation 0 1 2 3	4	NA			
b. Moderate muscle inflammation 0 1 2 3	4	NA			
c. Mild muscle inflammation 0 1 2 3	4	NA			
26. Myalgia 0 1 2 3	4	NA			
(Absent) (Maximum) Overall evaluation for the tota	ality of d	lisease activity			
Activity	5 WOSC	LE DISEASE			

IMACS Form 07a: Myositis Disease Activity Assessment Tool – 2005, Version 2, updated 2015

Page 3 of 3

Appendix 21. MMT-8

IMACS FORM 04: Manual Muscle Testing Scoring Sheet

Subject's IMACS number	
Assessor	
Date of assessment (mm/dd/y	/y)
Assessment number	

Muscle Groups	Right (0 - 10)	Left (0 - 10)	Axial (0 – 10)
Axial Muscles (0 – 20)			
Neck Flexors**	-	-	
Neck Extensors	-	-	
Proximal Muscles (0 - 160)			
Trapezius			-
Deltoid middle**			-
Biceps brachii**			-
Gluteus maximus**			-
Gluteus medius**			-
Iliopsoas			-
Hamstrings			-
Quadriceps**			-
Distal Muscles (0 - 80)			-
Wrist Extensors**			-
Wrist Flexors			-
Ankle dorsiflexors**			-
Ankle plantar flexors			-
MMT8 score** (0 - 80)			
Total MMT26 score (0 - 260)			

**MMT8 is a set of 8 designated muscles tested unilaterally (potential score 0 – 80), generally on right side (unless cannot be tested on right, then use left side) Axial score: 0 – 20 potential range: sum of neck flexors and extensors Proximal score: 0 - 160 potential range; 8 muscle groups tested bilaterally Distal score: 0 - 80 potential range; 4 muscle groups tested bilaterally Total score (MMT26): 0 - 260 potential range; sum of axial, proximal and distal scores

IMACS Form 04: Manual Muscle Testing Scoring Sheet

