In Amendment 4, an additional DM cohort of 8 to 16 participants with active moderate muscle involvement (MMT-8 \leq 136/150) will be enrolled. This cohort is referred to as Stage 3. Participants in this cohort are allowed to have any amount of skin involvement, as no specific CDASI score is required. All participants who meet eligibility criteria for (Stage 3) will be randomized to receive either PF-06823859 600 mg active study drug or placebo. This study design is similar to the Amended Stage 2 as all participants will receive their dosing assignment at Day 1 in a fixed sequence manner for the duration of the treatment period. The treatment period will consist of 6 dosing's occurring at Day 1, Week 4, (Visit 4), Week 8, (Visit 5), Week 12 (Visit 6), Week 16 (Visit 7), and Week 20, (Visit 8). Each participant will receive 3 consecutive doses of active study drug and 3 consecutive doses of placebo. At Week 12 (Visit 6), participants will be switched to the opposite treatment arm from what they were randomly assigned to at Day 1, Week 4 and Week 8. The study design permits all participants to receive active study drug in a blinded manner. The dose change between active and placebo will provide each participant 12 weeks of active drug. The end of the treatment period is at Week 24, although the last dose is administered at the Week 20 visit (Visit 8). All participants will then enter a 4 month follow-up period (the interval between the last dose and the end of the follow-up period is 5 months).

If a participant meets eligibility criteria for both Amended Stage 2 and Stage 3, the participant will be enrolled in Stage 3 unless the enrollment maximum for Stage 3 has been reached, at which point the participant would enroll in the Amended Stage 2.

Amendment 5 contained updates specific to Germany only. Germany is following the contraceptive guidelines related to CTFG guidelines, see Appendix 24.

Amendment 6; participants currently active in the C0251002 study at the time the open label extension study (C0251008) is approved, will have the opportunity to receive 24 additional weeks of treatment. Study participants will be eligible if they have completed the treatment period up through and including Visit 9, Week 24 and have not had any significant protocol deviations, or safety events. The participant can also select to continue into the follow up period of the C0251002 study for completion instead of enrolling into open label extension C0251008.

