- Disease -modifying antirheumatic drugs (DMARD)s, (methotrexate, sulfasalazine, hydroxychloroquine, and leflunomide). Less frequently used medications include gold salts, azathioprine, and cyclosporine. Dose must be stable for 60 days prior to Day 1 and remain stable through Week 24.

4.5. Inclusion Criteria, Stage 3

- 1. Evidence of a personally signed and dated informed consent document indicating that the participant has been informed of all pertinent aspects of the study.
- 2. Male and or female participants between the ages of ≥ 18 and ≤ 80 years old at the time of signing the informed consent.
- 3. Meets one of the following two criteria:
- MMT-8 ≤136/150 and PhGA, VAS ≥3 cm (0-10 cm) by visual analog scale (VAS) (Appendix 21).
- Sum of PhGA, VAS, PtGA, and extramuscular global assessment VAS scores (Appendix 20) is ≥10 cm (0-10 cm) VAS for each).
- 4. Participant has failed at least two or more adequate courses of an immunosuppressive agent or immunomodulatory agent, including IVIG, at a dose known to be effective for rheumatologic diseases.
- 5. Participant has had a standard work up for dermatomyositis (prior to) baseline.
 - a. Stable interstitial lung disease related to DM that is not severe in the opinion of the investigator is allowed, ie, no supplemental oxygen permitted.
 - b. If their DM diagnosis is within 2 years of the screening visit, then they must have completed either:
 - Age appropriate malignancy screening eg, computerized tomography, (CT) of the chest/abdomen/pelvis if indicated;

or

- PET CT of chest/abdomen/pelvis at least once by the baseline visit.
- 6. Male participants able to father children and female participants of childbearing potential must agree to adhere to the methods of contraception. See Appendix 25 throughout the duration of the study, including the follow-up period until the end of study.
 - Participants in Germany: please see guidelines for Contraception Methods in Appendix 24.
- 7. Female participants of non-childbearing potential must meet at least 1 of the following criteria:
 - a. Achieved postmenopausal status, defined as follows: cessation of regular menses for at least 12 consecutive months with no alternative pathological or physiological cause; status may be confirmed with a serum follicle-stimulating hormone (FSH) level confirming the postmenopausal state.
 - b. Have undergone a documented hysterectomy and/or bilateral oophorectomy.
 - c. Have medically confirmed ovarian failure.

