7.6. Rater Qualifications

7.6.1. CDASI

The primary and secondary endpoints for this study assess changes in the modified CDASI,¹⁴ activity score as well as the individual components.

To ensure uniform conduct of the CDASI in participants with DM, investigators or other qualified site personnel will be required to go through training session(s) led by a qualified individual. Personnel responsible for conducting the CDASI will be permitted to complete CDASI assessments once training is completed and proper documentation of training is issued. It is highly recommended that the same individual conduct the CDASI assessment from visit to visit to decrease variability. It is also highly recommended that the same individual complete the Physician Global Assessment (PhGA, VAS) for consistency (See Appendix 3).

7.6.2. MMT-8 Stage 3

This partially validated tool assesses muscle strength using manual muscle testing (MMT). A 0 - 10 point scale is proposed for use. An abbreviated group of 8 proximal, distal, and axial muscles performs similarly to a total of 24 muscle groups, and is also proposed for use for research studies.

To ensure uniform conduct of the MMT-8 in participants with DM, investigators or other qualified site personnel will be required to go through training session(s) led by a qualified individual, or video training. Personnel responsible for conducting the MMT-8 will be permitted to complete MMT-8 assessments once training is completed and proper documentation of training is issued. It is highly recommended that the same individual conduct the CDASI assessment from visit to visit to decrease variability. (See Appendix 21).

7.6.3. MDAAT Stage 3

Global extramuscular disease activity is measured by the MDAAT, a tool with a comprehensive approach that assesses constitutional, cutaneous, skeletal, gastrointestinal, pulmonary, and cardiovascular activity. To ensure uniform conduct of the MDAAT in participants with DM, investigators or other qualified site personnel will be required to go through training session(s) led by a qualified individual, or video training. (See Appendix 20)

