How to calculate the improvement score: The absolute percent change ([final value – baseline value]/range \times 100) is calculated for each core set measure. For muscle eraymes, the most abnormal serum muscle enzyme level at baseline (creatine kinase, aldolase, alanine transaminase, aspartate aminotransferase, lactate dehydrogenase) is used. The enzyme range was calculated based on a 90% range of enzymes from natural history data (34,46), which for creatine kinase is 15 times the upper limit of normal (ULN), for aldolase is 6 times the ULN, and for lactate dehydrogenase, aspartate aminotransferase, and alanine transaminase is 3 times the ULN. The ULN is determined according to the individual laboratories in the participating centers. The ranges for physician global activity, patient global activity, manual muscle testing. Health Assessment Questionnaire, and extramuscular global activity are based on the instrument scale used (3,26). An improvement score is assigned for each core set measure based on the absolute percent change in the core set measure according to the definition. These individual core set measure improvement scores are then totaled among the 6 core set measures to give the total improvement score itself may also be compared among treatment arms on a trial. A total improvement score is between 0 and 100 corresponds to the degree of improvement, while higher scores corresponding to a greater degree of improvement.

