In Protocol Amendment 4, an additional DM cohort of 8 to 16 participants with active moderate muscle involvement (MMT-8 \leq 136/150) will be enrolled. This cohort is referred to as Stage 3. Participants in this cohort are allowed to have any amount of skin involvement, as no specific CDASI score is required. All participants who meet eligibility criteria for (Stage 3) will be randomized to receive either PF-06823859 600 mg active study drug or placebo. This study design is similar to the Amended Stage 2 as all participants will receive their dosing assignment at Day 1 in a fixed sequence manner for the duration of the treatment period. The treatment period will consist of 6 dosing's occurring at Day 1, Week 4, (Visit 4), Week 8, (Visit 5), Week 12 (Visit 6), Week 16 (Visit 7), and Week 20, (Visit 8). Each participant will receive 3 consecutive doses of active study drug and 3 consecutive doses of placebo. At Week 12 (Visit 6), participants will be switched to the opposite treatment arm from what they were randomly assigned to at Day 1, Week 4 and Week 8. The study design permits all participants to receive active study drug in a blinded manner. The dose change between active and placebo will provide each participant 12 weeks of active drug. The end of the treatment period is at Week 24, although the last dose is administered at the Week 20 visit (Visit 8). All participants will then enter a 4 month follow-up period (the interval between the last dose and the end of the follow-up period is 5 months).

If a participant meets eligibility criteria for both Amended Stage 2 and Stage 3, the participant will be enrolled in Stage 3 unless the enrollment maximum for Stage 3 has been reached, at which point the participant would enroll in the Amended Stage 2.

The overall duration of the study will be approximately 69 months from first subject first visit, (FSFV) to last subject last visit, (LSLV) and will be conducted at approximately 35-40 investigative sites. Overall, approximately 76 participants will be randomized into this study.

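### The Stage 3 cut-off of MMT-8 ≤136/150 cannot work on the 0-80 one-sided form it cites, and the MMT range for the TIS is never given as a number

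*Protocol*

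**What the plan says.** Stage 3 inclusion criterion 3 (Protocol Section 4.5) is met by either of two routes. Route 1 reads "MMT-8 ≤136/150 and PhGA, VAS ≥3 cm (0-10 cm) by visual analog scale (VAS) (Appendix 21". Route 2 starts "Sum of PhGA, VAS, PtGA, and extramuscular global assessment VAS scores (Appendix 20", requires a total of at least 10 cm, and has no MMT-8 element.

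Protocol Section 3.1 describes Stage 3 as "an additional DM cohort of 8 to 16 participants with active moderate muscle involvement" and attaches the 136/150 figure. SAP 2.2 repeats both the description and the figure.

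Appendix 21, the form that route 1 cites, says "MMT8 is a set of 8 designated muscles tested unilaterally", generally on the right, and its score line is "MMT8 score (0 - 80". Protocol Section 7.6.2 gives a 0-10 scale per muscle and says "An abbreviated group of 8 proximal, distal, and axial muscles performs similarly to a total of 24 muscle groups", but states neither laterality nor a total.

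For the TIS, Section 7.9 names the MMT-8 score as one of six components. Appendix 22 and SAP 9.8 divide each change by the range of the measure. Enzyme ranges are given as multiples of the upper limit of normal. For the other five measures, MMT among them, the text says only that the ranges, down to that for "extramuscular global activity are based on the instrument scale used". No number is attached.

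**The concern.** One name covers two different scores. A site that follows the cited appendix records a value between 0 and 80 and then compares it with 136. The comparison is always satisfied, so the only muscle-strength condition in the entry criteria of a muscle cohort does nothing, and route 1 reduces to the PhGA condition.

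The same ambiguity reaches the efficacy analysis in two places. Protocol Section 9.1.3 makes TIS the major Stage 3 efficacy endpoint, and MMT carries up to 32.5 of its 100 points, more than any other item. With 80 and 150 both in the protocol, the programmer has no stated denominator. SAP 6.3.2.2 also analyses MMT-8 in its own units, by LANCOVA on change and by MMRM on absolute values. If sites scored on different bases, a participant at full strength would be 80 at one site and 150 at another, and that analysis would mix units.

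A smaller, separate mismatch is that Section 3.1 and SAP 2.2 describe the whole cohort by the 136/150 figure, although route 2 admits participants with no MMT-8 requirement.

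**Working it through.** **Inputs.** Starred muscles and the 0-80 range: Appendix 21. Points per muscle, 0-10: Section 7.6.2. Cut-off 136/150: Sections 4.5 and 3.1, SAP 2.2. TIS formula and bands: Appendix 22, SAP 9.8. Participants per arm, 4 to 8: Section 9.1.3.

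**1. Both totals can be reproduced.** The form stars 1 axial muscle (neck flexors), 5 proximal and 2 distal, which makes 8.
- One side: 8 × 10 = 80, the form's range.
- Both sides for the 7 paired muscles, plus neck flexors once: 7 × 2 × 10 + 10 = 150, the denominator of the cut-off.

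Each is sound alone, but they are different scores.

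**2. Cut-off against each scale.** On 0-80 the maximum is below 136, so all 81 whole-number scores pass. On 0-150 the 14 scores from 137 to 150 fail. As a share of range, 136/150 = 90.7%, and 0.907 × 80 ≈ 72.5. This last figure is only a conversion; neither document states it.

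**3. TIS item under each range.** Percent change = (final − baseline) / range × 100. The MMT bands are: up to 2% scores 0; above 2% to 10% scores 10; above 10% to 20% scores 20; above 20% to 30% scores 27.5; above 30% scores 32.5. The band edges in raw points are 1.6, 8, 16 and 24 for a range of 80, and 3, 15, 30 and 45 for a range of 150.

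| Raw gain | Item score, range 80 | Item score, range 150 | Difference |
|---|---|---|---|
| 1 | 0 | 0 | 0 |
| 2-3 | 10 | 0 | 10 |
| 4-8 | 10 | 10 | 0 |
| 9-15 | 20 | 10 | 10 |
| 16 | 20 | 20 | 0 |
| 17-24 | 27.5 | 20 | 7.5 |
| 25-30 | 32.5 | 20 | 12.5 |
| 31-45 | 32.5 | 27.5 | 5 |
| 46-80 | 32.5 | 32.5 | 0 |

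Gains affected: 2 + 7 + 8 + 6 + 15 = 38 of 80. Sum of differences: 2×10 + 7×10 + 8×7.5 + 6×12.5 + 15×5 = 300. Mean over all 80 gains: 300/80 = 3.75 points.

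**4. Direction of a mixed pair.** A 0-80 score divided by 150 is under-scored by these amounts. A 0-150 score divided by 80 is over-scored by the same amounts at the same 38 gains.

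**5. Near the cut-off.** At 72/80 at most 8 points can be gained, and only gains of 2 and 3 change, each from 10 points to 0.

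**6. Matched pairs agree.** A gain of one point per muscle is 8/80 = 10% or 15/150 = 10%, and scores 10 either way. Two points per muscle is 16/80 = 30/150 = 20%, and scores 20 either way. Mixed, the two-sided gains give 15/80 = 18.75% (scores 20) and 30/80 = 37.5% (scores 32.5).

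**7. Effect on an arm mean.** One 10-point error shifts the mean by 10/4 = 2.5 with 4 per arm, or 10/8 = 1.25 with 8 per arm.

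**The case against.** The strongest reply is that the criterion carries its own denominator. It says out of 150, the form has right and left columns from which a 150-point total can be built, and MMT-8 raters must complete documented training. A rater holding a score out of 80 might well notice the mismatch. This makes two-sided scoring the likely intention, but it does not change the text. The form defines MMT-8 as one-sided, the criterion sends the reader to that form, and no passage overrides it. The training content is not in the documents.

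On the TIS, the plan's rule that the range follows the instrument scale implies a matched pair, and a matched pair gives no error. That stands: the TIS distortion is conditional on a mismatch, and nothing in the documents shows that one occurred or that sites differed.

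The 3.75 average weights all gains equally, and gains of 25 to 45 supply half of it (6×12.5 + 15×5 = 150 of 300). Those gains need a baseline of 55/80 or lower. It describes the scoring table and is not an estimate of bias. The arm-mean shifts are also modest beside the Table 3 half-widths: 2.5 against 17.4 to 29.1 with 4 per arm, and 1.25 against 12.3 to 20.6 with 8 per arm.

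Finally, the Stage 3 primary endpoint is safety, no hypothesis is tested and no p-values are given. That limits the consequence but does not make the cut-off work.

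**Conclusion.** The concern holds and should be fixed. The unconditional part is the entry rule: on the form it cites, the MMT-8 cut-off excludes nobody. PhGA still restricts route 1, and route 2 is unaffected because it never used MMT-8.

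The second part is that neither document gives the MMT range as a number, although MMT is the heaviest TIS item. The resulting error is zero if score and range share a scale. If they do not, it is 5 to 12.5 points at 38 of the 80 possible one-sided gains. These figures assume whole-point scores and the bands as printed.

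The mismatch between the cohort description and route 2 is minor and would not justify action by itself.

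**What to change.** Reconcile criterion 3, Sections 3.1 and 7.6.2, Appendix 21 and SAP 2.2 to one stated MMT-8 scale and laterality. The cut-off's denominator is consistent with two-sided testing on 0-150, but the choice is the sponsor's and no eligibility rule is proposed here. State the same number as the MMT range in Appendix 22 and SAP 9.8, and use one unit in the SAP 6.3.2.2 analysis.

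Check which scale the recorded Stage 3 scores used. Re-derive scores only where both sides were recorded, and list the rest as not convertible, because a one-sided record cannot yield a two-sided total.

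In the same amendment, align the cohort description in Section 3.1 and SAP 2.2 with the second entry route.

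The cost is a protocol clarification, one SAP line for the range, and a check of the MMT-8 forms for 8 to 16 participants.
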